	Dose modification guidelines for rociletinib and MPDL3280A are described in Section 5.7.

Concomitant Medications	Concomitant therapy includes any prescription or over-the-counter medications or preparations used by a patient from 28 days prior to the first dose of study treatment through 28 days after the last dose of study treatment, or the date of administration of subsequent anticancer therapy, whichever is earlier. All concomitant medications should be reported to the Investigator and recorded. Guidelines for use of concomitant medications are detailed in Section 7.							
W/4h dwarral								
Criteria	 Consent withdrawal at the patient's own request or at the request of their legally authorized representative; 							
	• Clinical disease progression where the Investigator believes that the patient will not continue to benefit from study treatment (Note: patients will be permitted to continue study treatment after a radiographic progression [Appendix A and Appendix B] if the benefit-risk ratio is judged to be favorable and continued treatment is approved by the Medical Monitor);							
	• Any event, adverse or otherwise, that, in the opinion of the Investigator, would pose an unacceptable safety risk to the patient;							
	• An intercurrent illness that, in the opinion of the Investigator, would affect assessments of the clinical status to a significant degree and requires discontinuation of therapy;							
	• A positive pregnancy test at any time during the study;							
	• Non-compliance as described in Section 5.5;							
	Investigator decision.							
	In addition, the Sponsor may discontinue the study early for any of the reasons noted in Section 12.6.							
Study Procedures	The Screening Period will be 28 days prior to the first dose of study treatment. Some assessments are required to be performed within shorter windows (eg, 7 or 14 days) prior to the first dose of study treatment (see Table 1). A mandatory baseline biopsy will be collected within 60 days prior to first dose of study treatment.							
	The Treatment Period will consist of 21-day treatment cycles. In Phase 1 only, there will be an additional 7-day Run-in-Period of rociletinib monotherapy. Clinic visits are scheduled on Day 1 of each cycle and more frequently during Cycle 1 (see Table 1).							

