namics	A mandatory fresh tumor tissue biopsy specimen will be collected within 60 days prior to the first day of study treatment for all patients. In addition, an optional fresh tumor biopsy may be collected at time of permanent treatment discontinuation due to disease progression (at the time the Investigator believes the patient is no longer deriving clinical benefit from study treatment, if treatment beyond radiographic disease progression is approved). The baseline tissue biopsy specimen from screening will be used for a retrospective confirmation of EGFR mutation status by a central laboratory. The baseline biopsy as well as the optional tissue biopsy collected at progression will also be used to investigate mechanisms of response, primary resistance, and acquired resistance to rociletinib and MPDL3280A. Blood samples will be collected for pharmacogenomic and pharmacodynamics analyses. The pharmacogenomic blood sample will be collected predose on C1D1 for genomic deoxyribonucleic acid (DNA) purification. The DNA sample may be evaluated by next generation sequencing (NGS), and molecular alterations in germline and tumor DNA may be compared so that molecular alterations unique to the tumor that may modulate response or resistance to EGFR targeted therapy can be unambiguously identified. Pharmacodynamic blood samples will be collected and processed as described in Table 2 and Section 8.4.5.
Statistical Procedures	Statistical methods are described in Section 10.

THIS PAGE IS INTENTIONALLY LEFT BLANK

Table 1: Study CO-1686-032 Schedule of Assessments

				Trea	tment Period			
	Screening Period	Rociletinib 7-day Run- In- Period (Phase 1 only)	Cycle 1 combination therapy (21-day cycle) Cycle 2+ combination therapy (21-day cycle)			End of Treatment ^C	Follow Up	
Procedure ^A	Day -28 to Day 0	Day 1 ^B	Day 1 ^B	Day 4	Days 8 and 15 ±2 days	Day 1 ±3 days		
Informed consent	Х							
Documentation of EGFR mutational status ^D	Х							
Medical/oncology history ^E	Х							
Physical examination	Complete ^{F,G}	Limited ^H	Complete ^G	Limited ^H	Limited ^H	Limited ^H	Complete ^G	
ECOG performance status ^I	X ^F	Х	Х			Х	Х	
Vital signs ^J	\mathbf{X}^{F}	X	Х	Х	X	Х	Х	
Hematology (including reticulocytes) ^K	X ^F	Х	X		X	Х	X	
Coagulation tests ^L	\mathbf{X}^{F}							
Urinalysis ^M	Х							
Fasting_serum chemistry ^N	X ^F	Х	Х			Х	Х	
Fasting blood glucose ⁰				Х	X			
Serum pregnancy test ^P	Х						Х	
Hemoglobin A1c	Х					Odd cycles		
TSH, free T_3 and free T_4^Q	Х					Х	Х	

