HIV/HBV/HCV serology ^R	Х							
ECHO/MUGA ^s	Х							
12-lead ECG ^T	\mathbf{X}^{F}	Х	X	X	X	X	X	
Pulmonary function test ^U	X							

			Treatment Period					
	Screening Period	Rociletinib 7-day Run- In- Period (Phase 1 only)	Cycle 1 combination therapy (21-day cycle) Cycle 2+ combination therapy (21-day cycle)			Cycle 2+ combination therapy (21-day cycle)	End of Treatment ^C	Follow Up
Procedure ^A	Day -28 to Day 0	Day 1 ^B	Day 1 ^B	Day 4	Days 8 and 15 ±2 days	Day 1 ±3 days		
Tumor biopsy ^V	Х						X ^{C,V}	
Tumor assessments ^W	Х					Х	$\mathbf{X}^{\mathrm{C},\mathrm{W}}$	
Pharmacogenomic blood sample (predose)		Х	X (Phase 2 only)					
Rociletinib PK sampling ^X		Х	Х		Days 8-9	X (see Table 2)	X ^{C,X}	
MPDL3280A PK sampling ^x			X			X (see Table 2)	X ^{C,X}	Х
ATA testing ^X			Х			X (see Table 2)	X ^{C,X}	Х
TBNK blood sample ^X	X ^F		Х		X		X ^{C,X}	
Pharmacodynamic blood sample ^X	Х		X		Day 8	X (see Table 2)	X ^{C,X}	
Dispense rociletinib/ drug accountability/diary ^Y		Х	X			Х		
Rociletinib in-clinic administration ^Y		Х	X		Day 8	Х		
MPDL3280A administration ^Z			X			Х		
Adverse events ^{AA}	Х	Х	Х	Х	X	Х	Х	
Concomitant medications ^{BB}	X	Х	X	X	X	Х	X	
Survival assessment/ subsequent therapies ^{CC}							Х	X

ATA, anti-therapeutic antibody; ECG, electrocardiogram; ECOG, Eastern Cooperative Oncology Group; EGFR, epidermal growth factor receptor; HBV, hepatitis B virus; HCV, hepatitis C virus; HIV, human immunodeficiency virus; MUGA, multigated acquisition (scan); PK, pharmacokinetic; TBNK, T, B, and natural killer; TSH, thyroid-stimulating hormone.

А	Unless otherwise specified: Clinic visits for the specified assessments in Cycle $2+$ should be completed ± 3 days of the scheduled time point relative to C1D1.
	Assessments are to be performed prior to administration of study treatment, when applicable. All results must be reviewed by the Investigator prior to administration
	of study treatment. Perform assessments as scheduled on C1D4 (ie, no window) and assessments for C1D8 and C1D15 within ± 2 days of the scheduled time points.
В	Procedures required on Day 1 of Run-in-Period (Phase 1) or CIDI (Phase 2) may be omitted if completed < 3 days earlier during the Screening Period.
С	Patients will be asked to return to the clinic 28 days (+7 days) after the last dose of study treatment, or before the patient initiates another anticancer agent, if sooner,

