	especially during screening for study eligibility purposes. Additional consideration should be given to borderline ECOG performance status to avoid enrolling patients
	with significant impairment.
J	After the patient has been resting for at least 5 minutes, measure body temperature, heart rate, respiratory rate, and blood pressure. For the first infusion of
	MPDL3280A, measure vital signs within 60 minutes before, every 15 (\pm 5) minutes during the infusion, and 30 (\pm 10) minutes after the infusion. For subsequent
	infusions, vital signs will be collected within 60 minutes before the infusion, during the infusion if clinically indicated or if symptoms occurred in the prior infusion,
	and 1 hour $(\pm 10 \text{ minutes})$ after the infusion.
K	Includes hemoglobin, hematocrit, WBC and differential (with ANC), reticulocyte count, and platelet count. Hematology results must be reviewed by the Investigator
_	before administration of rociletinib and/or MPDL3280A.
L	Includes prothrombin time, international normalized ratio (INR), and activated partial thromboplastin time (aPTT). Patients known to require concomitant therapy
	with anticoagulants such as warfarin should also have INR monitored throughout the study.
Μ	Collect a freshly voided, clean sample and analyze by dipstick for protein, glucose, blood, pH, and ketones. If dipstick findings are abnormal, then a microscopic
	evaluation will be performed to assess the abnormal findings.
Ν	Includes total protein, albumin, creatinine, blood urea nitrogen (BUN) or urea, total bilirubin, alkaline phosphatase, alanine aminotransferase (ALT), aspartate
	aminotransferase (AS1), total cholesterol, tasting glucose, sodium, potassium, magnesium, chloride, calcium, phosphorus and uric acid. Fasting glucose must be
	measured after an 8-hour fast (no food or liquid other than water).
0	Fasting glucose must be measured after an 8-hour fast (no food or liquid other than water).
Р	Perform for females of childbearing potential \leq /days before first day of study treatment and at the EOT Visit. If the serum pregnancy test results are not available on
	the first day of study treatment, a urine pregnancy test can be performed on the first day of study treatment. A negative result must be confirmed by a physician before
	the first dose of study treatment.

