4.4 Patients or Partners of Patients of Reproductive Potential

Pregnancy is an exclusion criterion and females of childbearing potential must not be considering getting pregnant during the study. Female patients who are more than 2 years postmenopausal or have had a hysterectomy will not be considered of childbearing potential. Female patients of childbearing potential must have a negative serum pregnancy within 7 days prior to administration of the first dose of either study drug. If the serum pregnancy results are not available on first day of study treatment (Day of Run-in-Period for Phase 1; C1D1 for Phase 2), a urine pregnancy test can be performed on the first day of study treatment to confirm that the patient is not pregnant before dosing. Both values should be entered in the electronic case report form (eCRF). Another serum pregnancy test will be performed at the End of Treatment (EOT) Visit.

Women of childbearing potential must practice double-barrier methods of contraception during treatment and for 90 days after the last dose of either study drug. Adequate contraception is defined as double-barrier protection (ie, condom plus spermicide in combination with a diaphragm, cervical/vault cap, or intrauterine device). Birth control pills, birth control patches and/or injections of hormones to prevent pregnancy are not considered an adequate method of preventing pregnancy.

Men with a female partner of childbearing potential must have either had a prior vasectomy or agree to double-barrier methods of contraception during treatment and for 21 days after the last dose of either study drug to allow for clearance of any altered sperm.

Patients will be instructed to notify the Investigator if pregnancy of a female patient or a partner of a male patient is discovered to have occurred either during the patient's treatment or within 90 days (female patients) or 21 days (partners of male patients) after completion of treatment with rociletinib and MPDL3280A.

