9.5 Pregnancy or Drug Exposure During Pregnancy

If a patient becomes pregnant during the study, the Investigator is to stop dosing with study drug(s) immediately.

A pregnancy is not considered to be an AE or SAE; however, it must be reported to the Sponsor using the Pregnancy Report Form within the same timelines as an SAE (Section 9.9). This applies to female patients as well as female partners of male patients.

A pregnancy should be followed through to outcome, whenever possible. Once the outcome of the pregnancy is known, the Pregnancy Outcome Report Form should be completed and reported to the Sponsor.

AEs or SAEs that occur during pregnancy will be assessed and processed according to the AE or SAE processes using the appropriate AE or SAE forms.

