11 PATIENT DISPOSITION

11.1 Permanent Discontinuation of Study Treatment

A patient must be discontinued from all study treatment if any of the following applies:

- Consent withdrawal at the patient's own request or at the request of their legally authorized representative;
- Clinical disease progression where the Investigator believes that the patient will not continue to benefit from study treatment (*Note:* patients will be permitted to continue study treatment after a radiographic progression [Appendix A: and Appendix B] if the benefit-risk ratio is judged to be favorable and continued treatment is approved by the Medical Monitor);
- Any event, adverse or otherwise, that, in the opinion of the Investigator, would pose an unacceptable safety risk to the patient;
- Any requirement for dose holds of rociletinib for more than 14 days or dose holds of MPDL3280A for more than 42 days, unless permission from the Sponsor's Medical Monitor for longer dose delay is granted;
- An intercurrent illness that, in the opinion of the Investigator, would affect assessments of the clinical status to a significant degree and requires discontinuation of therapy;
- A positive pregnancy test at any time during the study;
- Investigator decision.

In addition, the Sponsor may discontinue the study early for any of the reasons noted in Section 12.6.

The Sponsor (or designee) should be notified of all study terminations as soon as possible. The date and reason for cessation of PO rociletinib and/or IV MPDL3280A must be documented in the eCRF and source documents.

To the extent possible, EOT assessments should be performed for all patients who receive rociletinib and MPDL3280A. The EOT visit should occur 28 (\pm 7) days after the last dose of rociletinib and MPDL3280A. After stopping protocol-specified treatment, all patients will remain in the study and will be followed for safety (through 28 days after last dose; those with ongoing SAEs will be followed until either resolution or stabilization has been determined), for disease progression (every 8 \pm 1 weeks until disease progression), and for survival status and subsequent NSCLC therapies (at approximately quarterly intervals until death or Sponsor decision).

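### No pregnancy test is scheduled between first and last dose, so the rules that stop dosing for pregnancy have no scheduled trigger while the patient is on drug

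*Combined protocol and SAP*

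**What the plan says.** **Stop rules.** Section 11.1 opens with "A patient must be discontinued from all study treatment if any of the following applies", and its list includes "A positive pregnancy test at any time during the study". The synopsis withdrawal criteria carry the same item. Section 9.5 adds: "If a patient becomes pregnant during the study, the Investigator is to stop dosing with study drug(s) immediately".

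**Test schedule.** In Table 1 the serum pregnancy test is marked under Screening and End of Treatment only. Footnote P limits it to 7 days or less "before first day of study treatment and at the EOT Visit", and Section 8.4.2.2 gives the same two times. Section 4.4 places the only later test after treatment: "Another serum pregnancy test will be performed at the End of Treatment (EOT) Visit". If the serum result is not back on the first treatment day, a urine test may be done, but before dosing.

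**Timing of the EOT Visit.** Table 1, footnote C: "Patients will be asked to return to the clinic 28 days (+7 days) after the last dose of study treatment", or earlier if another anticancer agent is about to start. Either way it follows the last dose.

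**Other safeguards on drug.** Section 4.4: "Women of childbearing potential must practice double-barrier methods of contraception during treatment". The same section tells patients to report a pregnancy once it is discovered. Section 8.4.2.6 provides a physical examination at each visit, Section 9.1 a question about new symptoms, and Section 8.4.2.2 allows further tests at the investigator's discretion.

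**The concern.** The plan commits to stopping both drugs when pregnancy is found, but schedules no test at a time when stopping could still limit exposure. If contraception fails, twice-daily rociletinib and MPDL3280A every 3 weeks continue until the patient reports a pregnancy or someone suspects one and orders a test.

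Suspicion may come late. Section 1.3.1 reports treatment-related nausea in 28% and fatigue in 20% of patients on rociletinib, and Section 6.1.2 directs patients and sites to consider hyperglycemia when nausea, vomiting, anorexia or fatigue increase. Early pregnancy can present in the same way. Section 5.7.4 notes that MPDL3280A has no antidote and that stopping it may not act at once, so an infusion given before detection cannot be taken back.

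What is at stake is avoidable drug exposure in pregnancy. No efficacy result is affected.

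**Working it through.** The plan states no figure on this point, so there is none to reproduce. The check is a count of scheduled tests, followed by the gaps under the present and proposed schedules.

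**1. Scheduled tests, from Table 1, footnotes C and P, and Sections 4.4 and 8.4.2.2**

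| Period | Scheduled pregnancy tests |
|---|---|
| Before first dose | 1 serum (plus a conditional urine test before dosing) |
| First dose to last dose | 0 |
| After last dose | 1 serum, at EOT |

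Urinalysis does not fill the gap. It is scheduled at screening only, and the dipstick panel in Section 8.4.2.2 has no pregnancy marker.

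**2. Present on-drug interval without a scheduled test.** With no on-drug test, this equals treatment duration: 21k days for k cycles, plus 7 where there is a Phase 1 run-in.

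| Cycles k | Without run-in (21k) | With run-in (21k + 7) |
|---|---|---|
| 2 | 42 | 49 |
| 6 | 126 | 133 |
| 15 | 315 | 322 |

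The documents give no treatment duration for the combination, so k is an assumption. The value 15 approximates the cited single-agent median PFS: 10.4 months × 30.44 / 21 = 15.1 cycles. That PFS comes from patients with acquired resistance, and PFS is not treatment duration, so it is only a marker for the upper part of the range.

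**3. Age of the baseline test at the first MPDL3280A infusion in Phase 1.** Up to 7 days before Run-in Day 1, plus 7 days of run-in: 7 + 7 = 14 days, if C1D1 is not delayed.

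**4. Longest gap from the previous test, testing on Day 1 from Cycle 2 only.** Cycle 2+ visits have a window of ±3 days relative to C1D1.

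- Phase 2: 7 + 21 + 3 = 31 days.
- Phase 1 with run-in: 7 + 7 + 21 + 3 = 38 days.
- Between later tests: 21 + 3 + 3 = 27 days.

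A Phase 1 safety expansion cohort without run-in (Section 3.2.3) follows the 31-day figure.

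**5. With an added Phase 1 test at C1D1, or up to 3 days before it.** Baseline to this test is at most 14 days. From this test to C2D1 it is at most 3 + 21 + 3 = 27 days. The Phase 1 maximum falls from 38 to 27 days.

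**6. Added tests per woman.** From Cycle 2 the number is k − 1, or 1, 5 and 14 for 2, 6 and 15 cycles. Phase 1 patients with a run-in have one more.

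**7. False positives.** The rate is not in the documents. At an assumed 0.01% to 0.1% per test, with tests independent, the chance of at least one over 14 tests is 1 − 0.9999^14 = 0.14% to 1 − 0.999^14 = 1.39%.

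**The case against.** The best case for the plan is that this is a monitoring preference. The stop rules are not inoperative: a positive test at any time includes an unscheduled one, and Section 9.5 applies however the pregnancy is found. A negative result is required before dosing, hormonal contraception does not count as adequate, and patients are seen, examined and questioned every cycle. Scans that include the pelvis take place every 6 weeks through Cycle 6 and every 9 weeks thereafter. The right test frequency depends on embryo-fetal risk. The protocol gives no such data and refers to the Investigator's Brochures for nonclinical detail.

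Much of this stands. It keeps the priority low and leaves the exact frequency to the sponsor's clinicians. It does not remove the point, because contraception does not detect pregnancy, the other safeguards depend on someone suspecting it, and a scan does not replace an hCG test.

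A second objection is also sound. More testing under the present Section 11.1 would let one false positive permanently end treatment in advanced lung cancer, and a discretionary repeat would not undo a rule already met. Any added test therefore needs a confirmation step.

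Two stronger readings are tempting. A reader might infer that the protocol contradicts itself; it does not, since every section gives the same two test times and none promises a test during dosing. A reader might also take the intervals of 42 to 322 days as undetected exposure. They are only the time without a scheduled test, and the documents support no estimate of how many pregnancies would occur or how late they would be found.

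**Conclusion.** The concern holds as a cheap, low-priority patient-safety improvement. For women of childbearing potential, zero pregnancy tests are scheduled between first and last dose, so Sections 9.5 and 11.1 have no scheduled trigger during dosing. The count rests on the documents alone and needs no assumption.

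The benefit cannot be put as exposures avoided, because neither the number of women of childbearing potential nor their pregnancy risk is given. What can be stated is the schedule: from an untested interval as long as treatment itself to a longest gap of 31 days in Phase 2 and 38 days in Phase 1 with run-in (27 with a test at C1D1), and at most 27 days between later tests. These figures assume visits within their windows and no delay of C1D1.

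**What to change.** **Schedule.** In Table 1, footnote P, Section 4.4 and Section 8.4.2.2, add for women of childbearing potential a local serum pregnancy test on Day 1 of each cycle from Cycle 2, with the result reviewed before dosing. In Phase 1 also test at C1D1 before the first MPDL3280A infusion, or within 3 days before it.

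**Confirmation.** State in Section 11.1 and the synopsis that:

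- a positive on-treatment test leads to an immediate hold of both drugs and a prompt repeat serum test, for example within 3 days;
- a confirmed positive means permanent discontinuation;
- a negative repeat allows dosing to resume.

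**Holds.** Section 5.7.3 and Table 8 currently bar a rociletinib hold in Phase 1 Cycle 1 except for toxicity, and Table 8 bars any MPDL3280A hold there. Both should permit this brief hold. If the Phase 1 test is taken before C1D1, Section 5.7.2 and the run-in column of Table 8 need the same sentence. From Cycle 2, Section 5.7.4 already allows holds unrelated to toxicity (14 days for rociletinib, 42 for MPDL3280A).

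**Cost.** One inexpensive local assay per cycle in this subgroup, at visits where blood is already drawn for hematology and chemistry and results are already reviewed before dosing. No extra visit is needed; the laboratory should confirm sample volume and tube type. An occasional false positive would cause a brief hold: about 0.14% to 1.4% of women over 14 tests at the assumed rates.

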1 INTRODUCTION

Despite years of research and prevention strategies, lung cancer continues to be the most common cancer worldwide and the most common cause of cancer-related deaths worldwide,4 accounting for 1.8 million new cases and 1.6 million deaths in 2012. Lung cancer has a 5-year survival rate of less than 10% in patients with advanced disease.5

Activating epidermal growth factor receptor (EGFR) mutations are key drivers of non-small cell lung cancer (NSCLC) malignancy in 10% to 15% of patients of European descent and approximately 30% of patients of East Asian descent.6 The two most frequently detected EGFR mutations in NSCLC patients are in the kinase domain: L858R substitution in exon 21 and deletions in a specific amino acid motif in exon 19 (Del19). Following demonstration of improved response rates and progression-free survival (PFS) over cytotoxic chemotherapy in Phase 3 studies of erlotinib, gefitinib, and afatinib,7[,]8[,]9^{,10,11} treatment of such patients with EGFR inhibitors is now standard of care.

While the toxicity profile is also improved with first-generation tyrosine kinase inhibitors (TKIs) compared to chemotherapy, significant toxicities do occur. Toxicity associated with both erlotinib and gefitinib includes skin rash and diarrhea related to inhibition of the wild-type (WT, normal) EGFR in skin and intestine, respectively.^{12,13,14}

Despite the initial response, patients generally experience progression within 9 months to 14 months of starting erlotinib, gefitinib, or afatinib. After disease progression on an EGFR-TKI, patients are often treated with chemotherapy. A number of small studies report response rates of 14% to 18% and PFS of around 4 months on chemotherapy after failure of an EGFR-TKI.^{15,16}

Mechanisms of resistance commonly include acquisition of secondary activating mutations while the initial activating mutation is maintained.¹⁷ The most common cause of resistance is thought to be due to development of a second site EGFR mutation in exon 20 called T790M (the "gatekeeper" mutation), which prevents drug from binding to the receptor.^{17,18,19,20} In addition, resistance may be associated with amplification of the EGFR gene or other genes that drive tumor growth such as MET gene amplification and PI3K mutations. Second-generation TKIs such as dacomitinib, neratinib, and afatinib have demonstrated limited clinical activity when the T790M mutation is present possibly because the toxicity from potent WT EGFR inhibition limits dosing such that drug concentrations required to inhibit T790M are not achieved.²¹ Assessment of post-progression survival in patients treated with EGFR-TKI indicated that those with EGFR T790M mutation-positive (T790M+) tumors had a median post-progression survival of 1.9 years (95% CI, 1.6-2.6 years).²² Thus, NSCLC patients who have failed treatment with TKIs and whose tumors express T790M mutation represent a group with fatal disease and unmet need. Furthermore, methods to prevent the acquisition of the T790M mutation are desirable.

In addition to the development of acquired mutations, evasion of immune destruction has been found to be an important mechanism of tumorigenesis and disease progression. Programmed death 1 (PD-1) protein is a T-cell coinhibitory receptor and has two known ligands, PD-L1 (B7-H1) and PD-L2 (B7-DC). PD-L1 is selectively expressed on many tumors and on cells within the tumor microenvironment. Binding of PD-L1 to its receptors suppresses T-cell migration, proliferation and secretion of cytotoxic mediators, and restricts tumor cell killing.

Potentiation of immune responses has been observed via blockade of the interaction between PD-1 and PD-L1 and has resulted in antitumor activity in both nonclinical models and early clinical studies.

Recent studies suggest that activation of PD-1 pathway may contribute to immune escape in EGFR-driven tumors. PD-L1 is overexpressed in EGFR-mutated NSCLC cell lines and resected tumors. In addition, inhibition of EGFR signaling with erlotinib resulted in down-regulation of PD-L1 expression in EGFR-mutated NSCLC cells but not in those with WT EGFR. These and other data suggest that PD-L1 expression may be dependent on EGFR signaling via activating EGFR mutations. In a recent study, overexpression of PD-L1 was demonstrated in the presence of erlotinib in EGFR-TKI-resistant H195 cells, which harbor both an activating mutation and the T790 mutation. Thus, blockade of PD1- PD-L1 signaling may help to overcome acquired resistance to EGFR-TKIs.

Rociletinib is a novel, potent, small molecule TKI that irreversibly binds and inhibits EGFR with the common activating (L858R, Del19) and T790M-resistance mutations and has minimal activity towards WT EGFR. Clovis Oncology, Inc. (Clovis or Sponsor) is developing rociletinib as a therapeutic agent to be administered orally (PO) to patients with EGFRm NSCLC who have been previously treated with an EGFR-targeted therapy and have a T790M mutation in EGFR.

The recommended Phase 2 doses (RP2Ds) of single-agent rociletinib are 500 and 625 mg twice daily (BID), as determined in the Phase 1/2 study, CO-1686-008 in patients with advanced or metastatic EGFRm NSCLC previously treated with an EGFR inhibitor. In CO-1686-008, Response Evaluation Criteria in Solid Tumors, Version 1.1 (RECIST v1.1) responses have been observed across a range of doses of rociletinib (500 mg BID to 1000 mg BID), and the overall response rate (ORR) among NSCLC patients with the T790M+ treated with rociletinib at 500 mg or 625 mg BID, the Phase 2 clinical doses, was approximately 67%.1 Responses to rociletinib are rapid, frequently occurring within less than 12 weeks. The median PFS in patients receiving rociletinib monotherapy at 500 mg or 625 mg in the context of acquired resistance has been reported as 10.4 months.1 Responses have also been observed in T790M negative (T790M–) patients.1 The most common rociletinib-related adverse event (AE) observed in single-agent studies has been hyperglycemia, which is generally managed with oral anti-hyperglycemic therapy. AEs typically associated with the inhibition of WT EGFR (eg, the combination of rash and chronic diarrhea) have not been observed with rociletinib.

MPDL3280A is a human IgG1 monoclonal antibody consisting of two heavy chains (448 amino acids) and two light chains (214 amino acids) and is produced in Chinese hamster ovary cells. MPDL3280A was engineered to eliminate Fc-effector function via a single amino acid substitution (asparagine to alanine) at position 298 on the heavy chain, which results in a non-glycosylated antibody that has minimal binding to Fc receptors and consequently, eliminates detectable Fc-effector function and depletion of cells expressing PD-L1. MPDL3280A targets human PD-L1 and inhibits its interaction with its receptor, PD-1. MPDL3280A also blocks the binding of PD-L1 to B7.1, an interaction that is reported to provide additional inhibitory signals to T cells.2

The interaction of PD-L1 with PD-1 and B7.1 inactivates T cells and prevents further T cell priming, and increased PD-L1 expression on tumor cells and/or tumor-infiltrating cells is a mechanism of cancer evasion of immune surveillance.

In Phase 1 studies of MPDL3280A, the maximum tolerated dose (MTD) was not reached, and no dose-limiting toxicity (DLT) was reported. The most common observed AEs have been fatigue and decreased appetite. The RP2D of intravenous (IV) single-agent MPDL3280A has been identified as 1200 mg every 3 weeks.

Antitumor activity has been observed in single-agent studies of MPDL3280A at doses from 1 mg/kg to 20 mg/kg in multiple tumor types. Data for 53 patients with NSCLC (including squamous and non-squamous histologies) treated with MPDL3280A has been presented. A 23% ORR based on RECIST v1.1was reported.3 The response rate in patients with PD-L1 expression in infiltrating immune cells was 46%. Tumor responses occurred as early as the first assessment. PFS in this group was remarkable for a 45% PFS at a 24-week landmark assessment.3

Treatment of tumors with rociletinib often results in a pronounced reduction in tumor volume, likely resulting in the increase of tumor antigen expression, CD8+ T cell infiltration, and a decrease in immunosuppressive cytokines. However, the immune response may be limited due to increased expression of immunomodulatory proteins such as PD-1, PD-L1, and B7.1 on the surface of tumor and T cells. As such, it is anticipated that the combination of MPDL3280A to rociletinib will enhance the immune antitumor immune response via blockade of the inhibitory signaling resulting from the interactions of PD-L1 with PD-1 and B7.1.

Two independent mechanisms of action, each with promising activity in patients with NSCLC, the potential for complementarity of these mechanisms of action, and largely non-overlapping safety profiles provide strong rationale for the current study, which will examine the combination of rociletinib and MPDL3280A in patients with EGFRm NSCLC. The tolerability of the combination is expected to be acceptable given the minimal overlapping toxicity profile and the overall tolerability of the two agents in patients with previously treated advanced cancers.

